## Software:

All statistical analyses will be performed using statistical software SAS® (Statistical Analysis System, SAS-Institute, Cary NC, USA, Windows Version 9.4 or higher) in the SAS Grid environment.

The computer program Phoenix® WinNonlin® Version 8.0, or higher (Certara, L.P., Princeton, New Jersey, USA) could be used for PK data.

## 10 Study Participants

The subsections in this section include specifications for reporting participant disposition and treatment/study discontinuations. Additionally, procedures for reporting protocol deviations are provided.

### 10.1 Disposition of Participants and Discontinuations

Descriptive statistics will be used to summarize participant disposition based on the electronic case report form (eCRF) data.

The following information will be reported:

- Total number of participants screened (i.e. participants who gave informed consent)
- Number of participants who discontinued from the study prior to study intervention overall and grouped by the main reason (e.g. the failed specific inclusion or exclusion criteria, adverse event, lost to follow-up, death, progressive disease, withdrawal of consent and other)

- Number of re-screened participants
- Number of participants who received at least one dose of study intervention (ITT/SAF analysis set)
- Number of participants with treatment ongoing at the data cutoff date
- Number of participants off study treatment, grouped by main reason (treatment completed as per protocol, progressive disease, death, adverse event, lost to follow-up, protocol non-compliance, withdrew consent, other)
- Number of participants who re-initiated the study treatment and number of participants who discontinued the study intervention after re-initiation
- Number of participants with treatment ongoing
- Number of participants who completed/discontinued the study participation, with the associated main primary reason (study completed according to protocol, adverse event, lost to follow-up, protocol non-compliance, death, withdrew consent, other)

Percentages will be calculated based on the number of participants in the ITT/SAF population, except for the number of screened and re-screened participants where no percentage will be provided.

In addition, the number of participants in each analysis set defined in Section 8.2 will be summarized, overall and by region (Europe, North America, Asia), country within region and center.

The listing of participant disposition will include all participants (i.e. including screening failures, but not re-screened participants [at their screen failure time] which will be listed in a specific listing). The listing will include the following information: participant identifier, date of informed consent, included in the study (if not reason for exclusion), first/last study intervention date, date and reason off-treatment, date and reason off-study, population flags. When the reason such as reason off-treatment will be categorized as “Other, specify” or “Withdrew consent from treatment, specify”, the verbatim text as entered in the eCRF will be presented in the listing.

In addition, a listing of participants for which bintrafusp alfa has been reinitiated will be provided with the following information: participant identifier, date of first study intervention, date of last study intervention, reason for treatment termination, first and last re-initiation bintrafusp alfa administration date and status at end of treatment re-initiation including reason for treatment discontinuation, as applicable.

If any re-screened participants are observed, they will be presented in a specific listing which will include: participant identifier (identifier at inclusion in the study), date of informed consent at inclusion, date of first study treatment, initial participant identifier (identifier at screen failure), date of informed consent at screen failure, date and reason of screen failure. Note in case participants have been screened several times, all screening attempts will be listed.

In addition, for the assessment of COVID-19 impact on this study, number of participants in subgroup of pre/during/post COVID-19 study period according to each categorization method described in [Table 4](#) (Section 9) will be provided.

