## 8.2 Definition of Analysis Populations and Subgroups

### Screening Analysis Set (SCR)

All participants who signed the informed consent.

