### Intention-to-Treat Set (ITT)/Safety Analysis Set (SAF)

The Intention-To-Treat analysis set as well as the Safety Analysis Set include all participants who received at least 1 dose of bintrafusp alfa.

The ITT analysis set will be used for all analyses of demographics and baseline characteristics, efficacy, **CCI** and **CCI**. The SAF analysis set will be used for all exposure and safety analyses.

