### Immunogenicity analysis set (IMM)

All participants who received at least 1 dose of bintrafusp alfa and have at least one valid ADA result.

All immunogenicity analyses will be based on this analysis set.

Table 3 displays the use of the analysis sets in the different analyses:

**Table 3** Overview of the Analysis Set Used in the Analyses

Analyses	SCR	SAF	ITT	PK	PKADA	PKNAB	IMM
Disposition	✓						
Demographics			✓				
Baseline Assessments			✓				
Previous and Concomitant Therapies			✓				
Compliance and Exposure		✓					
Efficacy			✓				
Safety and Tolerability		✓					
Pharmacokinetics				✓	✓	✓	
CCI							
Immunogenicity							✓
CCI							

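### As worded, SAP 10.1 would express participants lost before treatment as a percentage of those treated, a set that excludes them

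*SAP*

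**What the plan says.** SAP 10.1 lists the rows of the disposition summary. The first is "Total number of participants screened (i.e. participants who gave informed consent"). The next is "Number of participants who discontinued from the study prior to study intervention overall and grouped by the main reason"; its example reasons include failed eligibility criteria, adverse event, death, progression, loss to follow-up and withdrawn consent. The number re-screened follows as a separate row, and then the rows on treated participants.

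The denominator rule is: "Percentages will be calculated based on the number of participants in the ITT/SAF population, except for the number of screened and re-screened participants", and for those two counts the sentence ends "where no percentage will be provided".

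Three other places in the SAP bear on this:

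- Section 8.2, ITT/SAF: "The Intention-To-Treat analysis set as well as the Safety Analysis Set include all participants who received at least 1 dose of bintrafusp alfa".
- Section 8.2, Screening set (SCR): "All participants who signed the informed consent".
- Table 3, titled "Overview of the Analysis Set Used in the Analyses": the Disposition row has one tick, under SCR.

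SAP Section 9 adds two general rules. Proportions use the analysis set of interest unless stated otherwise, and a re-screened person is counted once in SCR, at the latest screening.

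**The concern.** A percentage should have a denominator that contains the people in its numerator. The pre-treatment row counts people who never received a dose, while its prescribed denominator is restricted to people who did. The two groups do not overlap, so the result is not a proportion and has no upper limit of 100%.

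Table 3 points to a set that does contain these people, so the SAP gives a programmer two different instructions for the same table. What is at stake is the accuracy of one descriptive figure: how many consented participants were lost before treatment, and for which reasons.

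**Working it through.** **Inputs.** T is the number treated, planned as 141 (Protocol 9.2). S is the number who left before treatment. Neither document gives S or the number screened, so values of S are assumptions. As a check on the planning figure, the exact one-sided test with 141 participants and success at 22 or more responses gives alpha 0.0239 and power 0.8007 for 18% against 10%, which agrees with the stated 80%. That check only anchors T. The plan states no pre-treatment loss figure to reproduce.

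**Which rule governs the row.** Section 9 defers to specific statements, and Section 10.1 makes one, so ITT/SAF applies unless a row is exempted. The exemption names two counts. They correspond to two bullets, the number screened and the number re-screened. The pre-treatment discontinuations form a third bullet that is not named. Taken literally, the row therefore gets a percentage with denominator T.

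**Formulas.**

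- As written: S/T.
- On the Screening set: f = S/(S+T).
- Since S = fT/(1-f), the as-written figure is S/T = f/(1-f). This depends on f only, not on T.
- The inflation factor is (S+T)/T = 1/(1-f), which is above 1 whenever S > 0.

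**Results with T = 141 (S assumed):**

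| S | S+T | On Screening set, S/(S+T) | As written, S/T |
|---|---|---|---|
| 16 | 157 | 10.2% | 11.3% |
| 35 | 176 | 19.9% | 24.8% |
| 60 | 201 | 29.9% | 42.6% |
| 94 | 235 | 40.0% | 66.7% |
| 141 | 282 | 50.0% | 100.0% |
| 211 | 352 | 59.9% | 149.6% |

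With exact values of f: 0.10/0.90 = 11.1%, 0.20/0.80 = 25.0%, 0.30/0.70 = 42.9%, 0.50/0.50 = 100%.

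**By-reason rows.** If r people left for a given reason, the two versions are r/T and r/(S+T). Every reason is inflated by the same factor 1/(1-f), so the ranking and relative size of the reasons do not change.

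**The case against.** The strongest defence is that the exception was meant to cover the whole screening block. The pre-treatment bullet lies between the screened and re-screened bullets, and the evident purpose of the exception is to avoid percentages for people outside ITT/SAF. On that reading the row prints counts only and nothing is inflated. The table shells are not in the documents, so no one can say from them what was programmed. This reading is possible, but the sentence does not say it: it names two counts that match two other bullets. If counts only was the intention, the sentence still needs a phrase added.

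The second defence is that no information is lost, and this stands. The same summary reports the total screened, the pre-treatment losses and the size of each analysis set, and a listing covers all participants, including screening failures. The correct rate is one division away. That limits the harm but does not make the printed percentage right.

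Three stronger readings are tempting, and the documents do not support them:

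- A reader might infer that the error distorts the comparison with the 10% benchmark. The benchmark comes from a literature-based response-rate estimate (Protocol 9.2). Neither document uses a pre-treatment loss rate to judge comparability, and none is given for the benchmark studies.
- A reader might infer that the figure will be badly wrong or exceed 100%. Exceeding 100% needs more than 141 losses for 141 treated, and nothing in the documents suggests that number. At a loss of about 10% the difference is about one percentage point.
- A reader might treat the row as the screen-failure rate. It is broader, because it also includes deaths, adverse events and consent withdrawals before dosing.

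**Conclusion.** The point holds on the wording of SAP 10.1: the pre-treatment discontinuation rows, overall and by reason, would carry percentages over a set that excludes everyone in them, and Table 3 assigns disposition to a different set. The direction of the error is certain if the rule is applied literally, since f/(1-f) exceeds f for any loss above zero. Its size is conditional, because it depends on a number screened that the documents do not give.

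This is a minor reporting matter. Efficacy and safety analyses rightly use ITT/SAF, so the response rate, its exact test, the intervals, the time-to-event endpoints and the adverse event tables do not change.

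**What to change.** In SAP 10.1, do one of the following for the pre-treatment discontinuation rows:

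- use the Screening set as denominator, with each person counted once at the latest screening as Section 9 requires, and apply the same rule to the numerator so that someone who failed screening and was later treated is not counted as a loss; or
- extend the exception so that these rows print counts without percentages.

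Keep ITT/SAF for all rows after first dose. Then align the Disposition row of Table 3: SCR for the pre-treatment rows and ITT/SAF for the post-dose rows.

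The cost is one sentence in Section 10.1, one table entry and one denominator in the table program. No new data are needed.

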## 10.2 Protocol Deviations

*Analysis Set: ITT*

The following summary tables and listings of important protocol deviations will be provided:

- Frequency table per reason of important protocol deviations
- Listing of important protocol deviations which will include participant identifier, category of the deviation (e.g. inclusion/exclusion), and a description of the deviation.

Potential impact of COVID-19 pandemic in MS200647-0047 will be evaluated by an analysis of protocol deviations. The number of participants with important protocol deviations overall as well as all protocol deviations due to COVID-19 will be tabulated. A subject listing of participants with any missed treatment administrations, missed tumor assessments, and missed visits due to COVID-19 will also be provided.

## 11 Demographics and Other Baseline Characteristics

*Analysis Set: ITT*

### 11.1 Demographics

Demographic characteristics will be summarized using the following information:

- Sex: male, female
- Ethnicity: Hispanic or Latino, not Hispanic or Latino; Japanese, not Japanese
- Race:
  - For participants reporting one race only: White, Black or African American, Asian, American Indian or Alaska Native, Native Hawaiian or other Pacific Islander, Not collected at the site, Other.
  - For participants reporting several races, all combinations will be reported under ‘More than one race’ category.
- Age (years): summary statistics
- Age categories:
  - < 65 years, ≥ 65 years
  - 65-74 years, 75-84 years, ≥ 85 years

- Geographic Region: North America, Europe, Asia

Specifications for computation:

- Age [years]: (date of given informed consent - date of birth + 1) / 365.25  
The integer part of the calculated age will be used for reporting purposes.
- Investigator site codes will be used for the determination of the participant's geographic region.

Demographic characteristics including participant identifier, sex, race (including all reported races in case of "multiple" races, and details in case of "other" race), ethnicity, geographic region, age (years) will be presented in a listing.

## 11.2 Medical History

Relevant past and ongoing medical conditions at baseline will be summarized from the "Medical History Details" eCRF page, using the latest available version of Medical Dictionary for Regulatory Activities (MedDRA), preferred term (PT) as event category and MedDRA system organ class (SOC) body term as Body System category.

Medical history will be displayed in frequency tables, ordered by primary SOC and PT in alphabetical order. Each participant will be counted only once within each PT or SOC.

Listing of medical history including participant identifier, age, sex, race, preferred term, reported medical history term, start/end dates, related study condition, ongoing at screening and toxicity grade (when medical history is ongoing) will be presented.

## 11.3 Other Baseline Characteristics

### 11.3.1 Disease History

Information on disease characteristics collected on the "Disease History" eCRF page will be summarized as follows:

- Biliary Tract Cancer (BTC) subtype classification: Intrahepatic cholangiocarcinoma, Extrahepatic cholangiocarcinoma (perihilar vs distal cholangiocarcinoma) and Gallbladder cancer
- Tumor histology: Adenocarcinoma well differentiated, Adenocarcinoma moderate differentiated, Adenocarcinoma poorly differentiated, Adenocarcinoma unknown, Other
- Time since initial cancer diagnosis (months)
- Time since documented, locally advanced or metastatic disease (months)
- Time since last progression of disease prior to study entry (months)
- TNM classification at initial diagnosis and at study entry: each T, N, M category will be described (TX, T0, N1, etc.)

### 11.3.2 Vital signs at Baseline

The following vital signs at baseline will be collected from the “Vital signs” eCRF page and will be summarized:

- Height (cm)
- Weight at baseline (kg)
- Body Mass Index (BMI) (kg/m^2)

Specifications for computation:

$$\circ \text{ BMI (kg/m}^2\text{)} = \text{weight(kg)}/[\text{height(m)}]^2$$

Height, weight and BMI will be listed in the demographics listing (see Section 11.1).

### 11.3.3 ECOG Performance Status at Baseline

The ECOG Performance Status will be described from the data collected on the “ECOG Performance Status” eCRF page. It will be described at baseline by the frequency and percentage of participants in each category:

- 0: Fully active, able to carry on all pre-disease performance without restriction.
- 1: Restricted in physically strenuous activity but ambulatory and able to carry out work of a light or sedentary nature, e.g., light housework, office work.
- 2: Ambulatory and capable of all selfcare but unable to carry out any work activities. Up and about more than 50% of waking hours.
- 3: Capable of only limited selfcare, confined to bed or chair more than 50% of waking hours.
- 4: Completely disabled. Cannot carry on any selfcare. Totally confined to bed or chair.

5: Dead.

### 11.3.4 Skin status history

Skin status history is collected on the “Skin Status History” eCRF page and will be summarized by the frequency and percentage of participants having the following history of:

- Frequent sunburn (Yes, No, Unknown)
- Easy sunburn (Yes, No, Unknown)
- Skin cancer (Yes, No, Unknown)
- Significant UV exposure (Yes, No, Unknown)
- Photosensitivity due to skin disorder (Yes, No, Unknown)
- Photosensitivity due to medication (Yes, No, Unknown)
- Family history of skin cancer in first degree relative (i.e. parents, siblings and/or children) (Yes, No, Unknown)
- Number of participants having history of the skin conditions above (No condition, 1 condition, 2 conditions, 3 or more conditions)

A listing of skin status history will be provided.

### 11.3.5 Tumor Biopsy

Tumor Biopsy is collected on the “Tumor Biopsy” eCRF page, a listing of tumor biopsy will be provided including: participant identifier, age, sex, race, visit, collection date, sample type (fresh biopsy or archival tissue sample), sample identifier, sample type for tumor block and for tumor tissue the number of slides collected.

### 11.3.6 PD-L1 test

PD-L1 expression on tumor cells or on immune cells as collected at screening will be described using the following categories:

- <1%, ≥1%; <5%, ≥5%; <25%, ≥25%; <50%, ≥50% for TC
- <1%, 1-50, ≥50% for TC
- <1%, ≥1%; <5%, ≥5%; <25%, ≥25%; <50%, ≥50% for IC
- <1%, 1-50, ≥50% for IC

Listing will also be provided and include: participant identifier, age, sex, race, unique sample identifier, visit, collection date and PD-L1 expression.

## 12 Previous or Concomitant Medications/Procedures

*Analysis set: ITT*

## 12.1 Previous and concomitant medications

**Previous medications** are medications, other than study medications, which started before first study intervention. In case the date values will not allow to unequivocally allocate a medication to previous medication, the medication will be considered as previous medication.

**Concomitant medications** are medications, other than study medications, which are taken by participants any time on-treatment (on or after the first day of study intervention for each participant) or within 30 days after last dose of study drug OR the earliest date of subsequent anticancer drug therapies minus 1 day, whichever occurs first. In case the date values will not allow to unequivocally allocate a medication to concomitant medication, the medication will be considered as concomitant medication. All medications starting the same day as study drug will be considered as concomitant. Medications starting the 30th days after the last dose of study treatment will also be considered as concomitant.

Specific rules will be used to define if a medication/procedure is considered as a previous, concomitant or both previous and concomitant medication/procedure as detailed in [Appendix 2](#).

Concomitant and previous medications are reported on the “Concomitant Medications Details” eCRF page.

Summaries of previous and concomitant medications will present the number and percentage of participants by drug class and preferred term according to the WHO-Drug B3 dictionary. Drug class will be derived as ATC classification Level 2, and the preferred term will be taken as the preferred drug name. If multiple ATCs are assigned to a drug, all ATCs for that drug will be reported.

A participant will be counted only once within a given drug class and within a given drug name, even if he/she received the same medication at different times.

Previous and concomitant medications will be presented in listing and include: participant identifier, age, sex, race, preferred term, medication name as provided by the Investigator, start date, end date, dose, dose units, frequency, route, reason for the medication.

## 12.2 Premedications for bintrafusp alfa

Premedications are medications administered per protocol on the same day as, but prior to, the study intervention to mitigate potential infusion-related reactions.

As per protocol, the first 15 participants will not receive premedications (except if requested by Investigator) before first and second bintrafusp alfa infusions to establish whether mandatory use of premedication is required. If two or more Grade 2 infusion reactions are seen during the first 2 infusions for the first 15 participants (without medication), IDMC will determine if mandatory premedication is needed. Study enrollment will continue in parallel to this review and sites will be notified accordingly if premedication becomes required. If IDMC determines mandatory premedication is justified, premedication prior to each dose of bintrafusp alfa will be mandatory

for the first 2 infusions. After 2 infusions, premedication will be optional and at the discretion of the Investigator.

The number of participants receiving premedication will be summarized for each treatment visit based on “Premedication details” eCRF page. If the IDMC determines that mandatory premedication is required, then the table will be split into two columns, participants enrolled before vs after the review of the first 15 participants.

Percentages will be calculated on the number of participants who actually received an infusion at the associated visit.

Listing will also be provided including: participant identifier, age, sex, race, medication name, visit, date/time of study intervention, dose, dose units, and route.

### 12.3 Concurrent procedures

Concurrent procedures are reported according to the “Concomitant Procedures Details” eCRF page.

Concurrent procedures will be presented in a listing which will include participant identifier, age, sex, race, name of procedure (as provided by the Investigator), start date, end date, indication, reason for procedure and type of specimen collected. A flag will be displayed to identify each procedure as prior to treatment and on-treatment.

### 12.4 Previous anticancer treatments and procedures

The previous anticancer treatments and procedures are collected under the “Prior Anti-Cancer Drug Therapies Details” and the “Prior Anti-Cancer Surgeries Details” eCRF pages.

The number of participants in each of the following anticancer treatment categories will be tabulated:

- Participants with at least one type of previous anticancer treatment or procedure (i.e. drug therapy, radiotherapy or surgery)
- Participants with at least one previous anticancer drug therapy
- Participants with at least one previous anticancer radiotherapy
- Participants with at least one previous anticancer surgery

Following details for previous systemic anticancer drug therapy will also be summarized:

- Number of any previous anticancer therapy regimens: 0 / 1 / 2 / 3 /  $\geq$  4
- Number of previous lines of therapy for metastatic/locally advanced disease: 0 / 1 / 2 / 3 /  $\geq$  4 (categories will be data dependent)
- Intent of therapy: Neoadjuvant / Adjuvant / Metastatic or Locally advanced

- Best response of last treatment regimen: Complete Response (CR) / Partial Response (PR) / Stable Disease (SD) / Progressive Disease (PD) / Non-Complete Response/Non-Progressive Disease (non-CR/non-PD) / Not Assessable / Unknown / Not applicable.
- The time since completion of first-line (1L) of platinum-based treatment will also be summarized. Platinum-based treatment will be identified for participants who received at least one platinum-based drug (cisplatin, oxaliplatin or carboplatin) and at least one of the following drugs in the same regimen: gemcitabine, fluorouracil or capecitabine. The time since completion will be measured using the maximum stop date of any of platinum-based drug/gemcitabine/fluorouracil/capecitabine treatment (maximum start date will be used in case the stop date is not available).
- Number of participants per 1L regimen, e.g., cisplatin/gemcitabine, cisplatin/fluorouracil.

Previous anticancer drugs, previous anticancer radiotherapy, and previous anticancer surgery will be presented in separate listings:

- The previous anticancer drug listing will contain participant identifier, age, sex, race, regimen ID, preferred term, medication name, start date, end date, intent of therapy, best response, date of progression.
- The previous anticancer radiotherapy listing will contain participant identifier, age, sex, race, start date, end date, was prior radiotherapy to bone for palliation only, location of radiotherapy, total dose, number of fractions.
- The previous anticancer surgery listing will contain participant identifier, age, sex, race, date of surgery, name and location of surgery, curative intent of surgery (Y/N), and outcome of surgery.

